9.3.2. Unsolicited Adverse Events

The primary safety endpoint is the proportion of subjects reporting product-related AEs and SAEs in each study arm following the first dose of study product through Visit 7 (Week 24, Day 168). The number of subjects, the proportion of subjects who experienced unsolicited AEs and SAEs following the first dose of the study product through Visit 7 (Week 24, Day 168), and the 95% Blaker CIs for the proportion of subjects who experienced unsolicited AEs and SAEs related to study product through Visit 7 will be presented for the safety population and actual treatment group. In addition, the difference in proportions between the LACTIN-V arm and the Placebo arm and 95% Blaker CIs will be presented in [Table 125](#). The proportion of subjects in each treatment group who experience product-related AEs following the first dose of the study product through Visit 7 (Week 24 Day 168) will be tested using a Fisher's exact test at the 5% two-sided level of significance level without adjustment for multiplicity in the safety analysis population. See Section 6.1 for pseudocode for calculating p-values and CIs.

The proportion of subjects reporting at least one unsolicited adverse event will be summarized by MedDRA system organ class and preferred term for all subjects and each actual treatment group. Denominators for percentages are the number of subjects who received the study product being summarized. A 95% Blaker CI will be presented for each MedDRA system organ class and preferred term (Table 126). Adverse events by subject will be presented in Listing 20.

The following summaries for unsolicited adverse events will be presented by MedDRA system organ class, preferred term, and treatment group:

- Incidence and percentage of subjects by maximum severity and maximum relationship to study product, including Frequency (Event level) of events for all subjects and by actual treatment received (Table 127 and Table 128);
- The number of adverse events occurring in 5% of subjects in any treatment group will be presented by MedDRA system organ class, preferred term, and treatment group in Table 129;
- The number of subjects reporting adverse events occurring in 5% of subjects in any treatment group will be presented by MedDRA system organ class, preferred term and treatment group in Table 130;
- Subject listing of non-serious adverse events of moderate or greater severity (Table 131);
- Bar chart of total frequency of adverse events by severity and MedDRA system organ class (Figure 45);
- Bar chart of subject incidence of adverse events by severity and MedDRA system organ class (Figure 46);
- Bar chart of total frequency of adverse events by relationship to study product and MedDRA system organ class (Figure 47);
- Bar chart of subject incidence of adverse events by relationship to study product and MedDRA system organ class (Figure 48).

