3.2.2 Primary Safety Outcome Measure

The proportion of participants reporting product-related AEs and SAEs in each study arm through Visit 7 (Week 24, Day 168)

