9.3. Adverse Events

When calculating the incidence of adverse events (i.e., on a per subject basis), each subject will only be counted once and any repetitions of adverse events within a subject will be ignored; the denominator will be the total safety population using the actual treatment group. All adverse events reported will be included in the

summaries and analyses. All analyses in Section 9.3 will be performed in the safety analysis population using the actual treatment received.

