9.4. Deaths, Serious Adverse Events and other Significant Adverse Events

The primary safety endpoint is the proportion of subjects reporting product-related AEs and SAEs in each study arm following the first dose of study product through Visit 7 (Week 24, Day 168). The number of subjects, the proportion of subjects who experienced product-related AEs and SAEs, and the 95% Blaker confidence interval for the proportion of subjects who experienced product-related SAEs will be presented for each analysis population, actual treatment group, and study visit. In addition, the difference in proportions between the LACTIN-V arm and the Placebo arm and 95% Blaker confidence intervals will be presented. As noted in Section 9.3.2, the proportion of subjects in each treatment group who experience product-related AEs and SAEs following the first dose of the study product through Visit 7 (Week 24 Day 168) will be tested using a Fisher's exact test at the 5% two-sided level of significance level without adjustment for multiplicity in the safety analysis population (Table 125). See Section 6.1 for pseudocode for calculating p-values and CIs.

A listing of deaths and serious adverse events will be presented, which will include Subject ID, treatment group, Adverse Event Description, Study Day the Event became Serious, Reason Reported as an SAE, Relationship to Treatment, Alternate Etiology if Not Related, Outcome, and Duration of Event in days (Table 132).

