Table 122: Number and Percentage of Subjects Experiencing Solicited Local Events by Symptom, Severity, Week, and Treatment Group—Safety Population—LACTIN-V—Weeks 7-24

Table 123: Number and Percentage of Subjects Experiencing Solicited Local Events by Symptom, Severity, Week, and Treatment Group—Safety Population—Placebo—Weeks 1-6

Table 124: Number and Percentage of Subjects Experiencing Solicited Local Events by Symptom, Severity, Week, and Treatment Group—Safety Population—Placebo—Weeks 7-24

Table 125: Proportion of Subjects Reporting Product Related Unsolicited Adverse Events Following the First Dose of Study Product through Visit 7 by Treatment Group – Safety Population

Treatment Group	Number of Subjects with AEs n	Number of Subjects N	Proportion of Subjects with AEs	Proportion of Subjects with AEs 95% CI	Difference in Proportion of Subjects with AEs between LACTIN-V and Placebo	Difference in Proportion of Subjects with AEs between LACTIN-V and Placebo 95% CI	P-value*
LACTIN-V	x	x	0.xx	0.xx, 0.xx	0.xx	0.xx, 0.xx	0.xxx
Placebo	x	x	0.xx	0.xx, 0.xx	--	--	--
All Subjects	x	x	0.xx	0.xx, 0.xx	--	--	--

Notes: The denominator for proportions is based on the number of subjects enrolled in the respective treatment group and analysis population.

*P-value from the Fisher’s exact two-sided test at the .05 level of significance.

95% CI= 95% Blaker Confidence Interval

Table 126: Number and Percentage of Subjects Experiencing Unsolicited Adverse Events with 95% Confidence Intervals by MedDRA System Organ Class and Preferred Term, Dose Number, and Treatment Group - Safety Population

MedDRA System Organ Class	MedDRA Preferred Term	LACTIN-V (N=X)			Placebo (N=X)			All Subjects (N=X)		
		n	%	95% CI	n	%	95% CI	n	%	95% CI
Any SOC	Any PT	x	x	x, x	x	x	x, x	x	x	x, x
[SOC 1]	Any PT	x	x	x, x	x	x	x, x	x	x	x, x
	[PT 1]	x	x	x, x	x	x	x, x	x	x	x, x
	[PT 2]	x	x	x, x	x	x	x, x	x	x	x, x
[SOC 2]	Any PT	x	x	x, x	x	x	x, x	x	x	x, x
	[PT 1]	x	x	x, x	x	x	x, x	x	x	x, x
	[PT 2]	x	x	x, x	x	x	x, x	x	x	x, x

Notes: N = number of subjects in the Safety Analysis Population who received the specified treatment.

This table presents number and percentage of subjects.

A subject is only counted once per PT/timepoint.

95% CI= 95% Blaker Confidence Interval

Table 127: Number and Percentage of Subjects Experiencing Unsolicited Adverse Events by MedDRA System Organ Class and Preferred Term, Maximum Severity and Relationship—Safety Population

			All Subjects (N = X)								

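### Table 125 and the SAP 9.3.2 confidence-interval sentence limit the primary safety endpoint to unsolicited events; the protocol has no such limit and SAP Section 13 does not declare it

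*SAP*

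**What the plan says.** Protocol 3.2.2 sets the endpoint as "The proportion of participants reporting product-related AEs and SAEs in each study arm through Visit 7 (Week 24, Day 168"). Protocol 11.2, 11.3 and 11.6.3.1 and SAP 3.2.2 repeat it in substance. None of them separates solicited from unsolicited events.

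SAP 9.3.2, headed Unsolicited Adverse Events, opens with that same endpoint. It then attaches the 95% Blaker interval to "the proportion of subjects who experienced unsolicited AEs and SAEs related to study product through Visit 7". Its Fisher sentence tests "The proportion of subjects in each treatment group who experience product-related AEs following the first dose of the study product through Visit 7".

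SAP 9.4 refers back to 9.3.2, tests "the proportion of subjects in each treatment group who experience product-related AEs and SAEs following the first dose of the study product", and sends the result to Table 125. That table is titled "Proportion of Subjects Reporting Product Related Unsolicited Adverse Events Following the First Dose of Study Product through Visit 7 by Treatment Group". No other shell carries this p-value.

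SAP 9.3 adds two general rules. "All adverse events reported will be included in the" summaries and analyses, and for incidence "each subject will only be counted once and any repetitions of adverse events within a subject will be ignored".

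SAP Section 13 lists two changes from the protocol: the added ITT efficacy analyses and the revised mITT and CC definitions. Neither concerns safety.

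**The concern.** The solicited symptoms are AEs in these documents. Protocol 9.2.1 lists the same 17 symptoms among the AEs to be captured and requires a related or not-related call for every AE. Protocol 11.6.3 calls them solicited AEs, and SAP 9.3.1 records a new or worsened symptom as a solicited AE. A product-related solicited AE therefore meets the endpoint as the protocol defines it, but falls outside Table 125 as titled.

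Protocol 11.3 plans only two formal tests, and this is one of them. Vaginal discharge, the only effect that Protocol 2.3.1.1 puts in its most likely category, is a solicited symptom. A related discharge recorded only on the solicited side would not count in the primary safety comparison, and nothing in Section 13 would tell the reader so.

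**Working it through.** **Step 1. The passages side by side.**

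| Place | Events counted | Unsolicited limit |
|---|---|---|
| Protocol 3.2.2, 11.2, 11.3, 11.6.3.1 | related AEs and SAEs | none |
| SAP 3.2.2; opening of SAP 9.3.2 | related AEs and SAEs | none |
| SAP 9.3.2, interval sentence | related AEs and SAEs | stated |
| SAP 9.3.2, Fisher sentence | related AEs; SAEs not named | not stated; the heading implies it |
| SAP 9.4, Fisher sentence | related AEs and SAEs | not stated; refers to 9.3.2 and Table 125 |
| Table 125 title | related AEs | stated |

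The SAP 9.4 interval wording differs again: "95% Blaker confidence interval for the proportion of subjects who experienced product-related SAEs will be presented for each analysis population". No p-value is attached to it, so it is a lesser inconsistency.

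**Step 2. Can the planned outputs supply the wider count?** Relatedness appears in Tables 125, 127, 128, 131 and 132, Listing 20 and Figures 47 and 48, all for unsolicited AEs or SAEs. The solicited shells (Tables 108 to 124) and Listings 18 and 19 show severity or occurrence, and the listings flag treatment-emergence; none shows relatedness. So the shells as drawn cannot fill the wider numerator. That does not show that relatedness was not collected.

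**Step 3. Could the choice matter?** The plan gives no rate, sample size or power for the safety test, so there is no safety figure to reproduce. Its total of 228 belongs to the efficacy test and is not in dispute: 30% v 15% at 2:1 and 70% power, uncorrected, gives 68 + 136 = 204, and 204/0.9 = 226.7, hence 228 as a multiple of three. If all are treated, the arms are 228 × 2/3 = 152 and 228/3 = 76.

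For m women with an event, x of them on LACTIN-V, P(x) = C(152, x)·C(76, m − x)/C(228, m). The two-sided Fisher p sums P over all tables no more probable than the one observed. **Every event count below is an assumption** (LACTIN-V v placebo).

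| Related unsolicited only | Solicited-only women added | Wider count | p, narrow | p, wide |
|---|---|---|---|---|
| 8 v 4 | 15 v 8 | 23 v 12 | 1.00 | 1.00 |
| 15 v 8 | 15 v 8 | 30 v 16 | 1.00 | 0.86 |
| 30 v 15 | 15 v 8 | 45 v 23 | 1.00 | 1.00 |
| 8 v 4 | 14 v 0 | 22 v 4 | 1.00 | 0.046 |
| 15 v 8 | 18 v 0 | 33 v 8 | 1.00 | 0.044 |
| 30 v 15 | 20 v 0 | 50 v 15 | 1.00 | 0.043 |
| 8 v 4 | 34 v 8 | 42 v 12 | 1.00 | 0.049 |
| 15 v 8 | 37 v 8 | 52 v 16 | 1.00 | 0.046 |
| 30 v 15 | 37 v 8 | 67 v 23 | 1.00 | 0.046 |
| 22 v 4 | 15 v 8 | 37 v 12 | 0.046 | 0.17 |

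Rows 1 to 3 add about 10% to each arm (15/152 = 9.9%, 8/76 = 10.5%), and the conclusion does not move. Rows 4 to 6 are the smallest one-sided additions that reach p < 0.05: 9% to 13% of LACTIN-V women and no placebo women. Rows 7 to 9 need 22% to 24% against about 10%. The last row runs the other way: a narrow-count difference is diluted.

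**Step 4. The interval for the difference.** SAP 6.1, 9.3.2 and 9.4 ask for a Blaker interval for a difference in proportions, and the Table 125 footnote labels its intervals Blaker. The code in SAP 6.1.1 produces Blaker limits for a single proportion only. Its one interval for a difference is the Newcombe.

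**The case against.** The SAP can be read as consistent with itself. The 9.3.2 Fisher sentence sits under a heading that limits the section to unsolicited events, and elsewhere in that section plain references to adverse events point to unsolicited outputs such as Listing 20. SAP 9.4 refers back to 9.3.2 and to the same table. This stands. A reader might infer that the SAP holds two rival primary safety tests; the heading and cross-references do not support that. What remains is one narrowing of the protocol endpoint that Section 13 does not declare. The SAP 9.3 rule that all reported AEs enter the analyses does not settle it either, since it also governs the solicited tables.

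Protocol 11.6.3 does put solicited and unsolicited events on separate tracks. But it does so for general summaries, and the endpoint section that follows, 11.6.3.1, carries no limit.

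Related symptoms may not be lost. Protocol 9.2.1 has AEs, these symptoms included, captured on a CRF with a clinician's relatedness call. SAP 4.5.1 says a new or worse symptom is recorded as an AE, and SAP 4.1 has electronic memory-aid reports trigger evaluation and reporting. If most related symptoms reach the AE form, the two numerators largely overlap. This also stands; the documents do not say how often it happens.

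Finally, Protocol 2.1 and 2.3.1.1 report AEs evenly distributed between arms in earlier trials, which favours the rows where nothing changes. Those statements concern all AEs, not related ones, and the two applicator trials had 12 and 24 women, so they lower the expected effect without excluding one. Solicited AEs are in any case shown by arm with intervals in Tables 108, 110 and 112.

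**Conclusion.** The point holds as an undeclared narrowing of the primary safety endpoint. The protocol and SAP 3.2.2 count related AEs and SAEs of either kind; the 9.3.2 interval sentence and Table 125 count related unsolicited events only; Section 13 is silent.

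The size is unknown. It depends on the related-AE rates by arm and on how many related symptoms are recorded only as solicited, and neither is given. The calculations show that the choice can change the Fisher result in either direction under assumed imbalances and leaves it unchanged under equal additions. They predict nothing for this trial. A reader might infer that the plan hides a safety signal, or that relatedness of solicited events was never recorded; the documents support neither.

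This should be fixed but is not critical: the trial is screening rather than confirmatory, and solicited events are reported elsewhere. The mismatch over the interval for the difference is a valid secondary defect.

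**What to change.** Before unblinding, establish whether relatedness was recorded for solicited AEs.

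- **If it was:** use one numerator for the estimate, interval, difference and Fisher test in SAP 9.3.2, 9.4 and Table 125. Count a woman once if she has at least one product-related AE, solicited or unsolicited, or a product-related SAE, from first dose through Visit 7. Keep the unsolicited-only version as supplementary.
- **If it was not:** declare the unsolicited-only restriction in Section 13 as a departure from Protocol 3.2.2, 11.3 and 11.6.3.1, and label the Table 125 result accordingly wherever it is reported.
- **In either case:** replace the Blaker interval for the difference with a named two-sample interval, such as the Newcombe interval already coded in SAP 6.1.1.

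The cost is wording in SAP 6.1, 9.3.2, 9.4 and Section 13 and one revised shell. Because each woman is counted once, events need no de-duplication across the two sources. In the second case the numerator change is one line in Section 13 and a label.

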9.4. Deaths, Serious Adverse Events and other Significant Adverse Events

The primary safety endpoint is the proportion of subjects reporting product-related AEs and SAEs in each study arm following the first dose of study product through Visit 7 (Week 24, Day 168). The number of subjects, the proportion of subjects who experienced product-related AEs and SAEs, and the 95% Blaker confidence interval for the proportion of subjects who experienced product-related SAEs will be presented for each analysis population, actual treatment group, and study visit. In addition, the difference in proportions between the LACTIN-V arm and the Placebo arm and 95% Blaker confidence intervals will be presented. As noted in Section 9.3.2, the proportion of subjects in each treatment group who experience product-related AEs and SAEs following the first dose of the study product through Visit 7 (Week 24 Day 168) will be tested using a Fisher's exact test at the 5% two-sided level of significance level without adjustment for multiplicity in the safety analysis population (Table 125). See Section 6.1 for pseudocode for calculating p-values and CIs.

A listing of deaths and serious adverse events will be presented, which will include Subject ID, treatment group, Adverse Event Description, Study Day the Event became Serious, Reason Reported as an SAE, Relationship to Treatment, Alternate Etiology if Not Related, Outcome, and Duration of Event in days (Table 132).

9.5. Pregnancies

For any subjects in the Safety population who became pregnant during the study, every attempt will be made to follow these subjects to completion of pregnancy to document the outcome, including information regarding any complications with pregnancy and/or delivery. A listing of the total pregnancies, number of live births, and number of spontaneous abortions, elective abortions or still births will be presented ([Listing 21](#), [Listing 22](#), [Listing 23](#), [Listing 24](#), and [Listing 25](#)).

9.6. Clinical Laboratory Evaluations

Various clinical laboratory parameters are collected during follow-up, if indicated. The evaluations are: clean catch urine dipstick, urinalysis, rapid urine β hCG pregnancy test, HIV and syphilis serology, and vaginal swab for *N. gonorrhoeae*, *C. trachomatis*, and *T. vaginalis*. Since the laboratory evaluations are only performed if indicated, subject listings of the clinical laboratory results will be provided ([Listing 26](#) and [Listing 27](#)). Trichomoniasis and yeast vaginitis wet mount results will be provided in [Listing 28](#).

9.7. Vital Signs and Physical Evaluations

A complete physical examination, assessment of vital signs, and a pelvic examination will be performed at screening and symptom-directed examinations will be performed at all subsequent visits. Vital sign measurements include systolic blood pressure, diastolic blood pressure, pulse, respiration, oral temperature, height, and weight. Since the evaluations are symptom-driven from enrollment to the end of follow-up, subject listings will be provided for vital signs ([Listing 29](#)), physical exam findings ([Listing 30](#)), and pelvic exam findings ([Listing 31](#)). Abnormal discharge and cervical mucus characteristics are displayed by visit and treatment group in [Table 133](#), [Table 134](#), and [Table 135](#). Subject listings will be provided for abnormal discharge ([Listing 32](#)), and cervical mucus characteristics ([Listing 33](#)).

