Adverse effects that may be associated with LACTIN-V include those seen with other vaginally administered products, and include:

Most likely:

- Vaginal, genital or menstrual symptoms: vaginal discharge

Less likely:

- Gastrointestinal symptoms: abdominal (stomach area) pain, constipation, diarrhea, nausea, vomiting
- Urinary symptoms: needing to urinate urgently, needing to urinate at night and pain with urination
- Vaginal, genital or menstrual symptoms: genital itching, bleeding between menstrual periods, delayed menstrual periods, vaginal odor, vaginal burning sensation, vaginal irritation, vaginal bleeding, vaginal dryness, genital swelling, rash, vaginal candidiasis (yeast infection)
- Other symptoms: lower back pain

Rare but potentially life-threatening:

- Allergic reaction (including anaphylaxis) to the study product

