Follow-up visits are scheduled 4, 8, 12 and 24 weeks after enrollment. A memory aid to gauge symptoms and AEs will be reviewed, a questionnaire to collect clinical, including AEs, data will be administered and a pelvic exam will be performed to detect genital tract AEs. Vaginal swabs for wet mount evaluation (Amsel criteria) and Gram stain evaluation (Nugent score) will be collected. A vaginal swab for *L. crispatus* (including CTV-05) identification will be collected. Vaginal applicators will be collected at Visits 2, 3, and 4 and stained with Trypan Blue upon return to the site as a proxy for product use. Telephone interviews will be scheduled between the 12 and 24 week visits, at 16 and 20 weeks after enrollment.

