11. Participants will be given a memory aid or a web link (with a username and temporary password) and instructed to make an entry following each insertion of a pre-filled applicator beginning with the first application at Visit 1 (Day 1). Any symptoms that occur during the study up until Visit 7 (Week 24, Day 168) will be recorded on the memory aid. Participants not using the web link will be reminded to return with the paper memory aid at each study visit where it will be reviewed.
12. Participants will be instructed to abstain from sexual intercourse during the first 5 days of study product administration, for 12 hours after the weekly study product applications and 12 hours before study Visit 2 (Week 4, Day 28), Visit 3 (Week 8, Day 56), Visit 4 (Week 12, Day 84) and Visit 7 (Week 24, Day 168).
13. Participants will receive non-spermicidal lubricated condoms for their male sexual partners who will be encouraged to use condoms from Visit 1 (Day 1) through Visit 7 (Week 24, Day 168) if they engage in vaginal intercourse.
14. Participants will be instructed not to use scented tampons or any other vaginal products through Visit 7 (Week 24, Day 168).
15. Participants will be advised to return for Visit 2 (Week 4, Day 28), Visit 3 (Week 8, Day 56) and Visit 4 (Week 12, Day 84) with allowable scheduling within 7 days of the target date. Depending on the time of the enrollment and the average length of the woman's menstrual cycle, careful attention should be paid to the approximate time of her next menstrual period when scheduling those visits. Later adjustments of those dates may be necessary.
16. Participants will be asked to collect all used applicators and store them as described in the MOP.
17. Participants will be asked to return all used applicators at their next visit.

Participants immediately diagnosed with yeast on the wet mount (with or without discharge or vaginitis symptoms) during the enrollment visit will be referred for standard treatment. They will not be randomized and will not be invited for rescreening.

If available test results at the enrollment visit suggest a UTI, cervicitis, vulvovaginitis, or active genital herpes lesion, the woman will be managed as clinically indicated and not randomized at this time, but invited for rescreening after completion of treatment.

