7.3 Follow-up Study Visit 2, Week 4, Day 28 (Allowable Days 21-35)

The following procedures and assessments will be performed at Visit 2, Week 4, Day 28:

1. Participants will return on Day 28. Staff will review the memory aid with the participant. The participant will be asked about symptoms, concomitant medications and any medical problems since the last visit, which will be recorded on the appropriate CRF. The participant will be asked to provide exact dates and times of the study product administration.
2. Medical, gynecological and sexual history to include assessment of STI and HIV risk
3. Symptom-directed physical and pelvic examination by a study physician or nurse that will include vital signs, including temperature, and examination of respiratory and cardiovascular systems, as well as assessment of symptoms and adverse events
4. The pelvic examination will be conducted in the following order:
 - a. Examination of the external genitalia
 - b. Speculum insertion and examination of vagina, fornices and cervix with naked eye. Water will be used to ease speculum insertion. No lubricant should be used as it could contain chlorhexidine which may kill *Lactobacillus*.
 - c. Vaginal pH
 - d. Vaginal swab for wet mount taken from the posterior fornix for yeast vaginitis and clue cells and for amine test (whiff test)
 - e. Vaginal swab for Gram stain (Nugent scoring system)
 - f. Vaginal swabs (no more than two) for storage and future identification of vaginal bacteria, and possible multiomic (e.g. proteomics, metabolomics, etc.) testing
 - g. Vaginal swabs for *L. crispatus* identification with qPCR
 - h. If indicated, cervical (or vaginal) swab for nucleic acid amplification of *N. gonorrhoeae*, *C. trachomatis*, and *T. vaginalis*
5. If indicated, clean catch urine dipstick; urinalysis if abnormal results indicate
6. If indicated, urine β hCG pregnancy test
7. All clinical and laboratory findings at the time of the evaluation will be recorded on the CRF. These findings will include observations present on the pelvic exam such as genital findings including location; presence or absence, and character of vaginal or cervical discharge or lesions; and results of any on-site tests.
8. Participants will be reminded not to use scented tampons or any other vaginal products through Visit 7 (Week 24, Day 168).

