APPENDIX B (Cont'd)
DIVISION OF AIDS TABLE FOR GRADING THE SEVERITY OF
ADULT AND PEDIATRIC ADVERSE EVENTS PUBLISH DATE: DECEMBER 2004

Addendum 1
Female Genital Grading Table for Use in Microbicide Studies

INFECTIONS AND DYSPLASIA				
PARAMETER	GRADE 0 NORMAL	GRADE 1 MILD	GRADE 2 MODERATE	GRADE 3 SEVERE
GENITOURINARY INFECTIONS				
Genital herpes	No lesions	Characteristic ulcerative or vesicular lesions confirmed by culture, PCR, Tzanck prep or other diagnostic test of lesion or previous type-specific serology, covering < 25% of vulva, vagina, or cervix	Same criteria as mild but covering 25-50% of vulvar, vaginal, or cervical surface	Same criteria as mild but covering > 50% of vulvar, vaginal, or cervical surface and/or symptoms of significant systemic involvement, e.g., encephalitis, hepatitis
Candida	Absence of symptoms regardless of candida test results	Positive culture, wet mount, or other laboratory test for yeast, with mild symptoms	Positive culture, wet mount, or other laboratory test for yeast, with moderate to severe symptoms	NA
Trichomonas	Negative	NA	Positive wet mount, culture, PCR or other licensed test, excluding pap smear, showing T. vaginalis, regardless of symptoms	NA
Bacterial Vaginosis (BV)	Negative	Asymptomatic BV diagnosed by Amsel criteria, wet mount, Gram stain, or licensed diagnostic test	Symptomatic confirmed by wet mount, Gram stain, or any licensed diagnostic test	NA
Chlamydia	Negative	NA	Positive culture or other diagnostic test for Chlamydia, asymptomatic or with mild uterine or cervical motion tenderness (no signs of peritoneal irritation)	Positive test for Chlamydia with abdominal or uterine or adnexal tenderness on examination, with or without adnexal mass, diffuse tenderness, any signs of peritoneal irritation, or indications for hospitalization (other than emergency room visit) including tubo-ovarian abscess

NOTE: For protocols utilizing this Addendum, when the same parameter appears in both this Female Genital Grading Table and the main DAIDS AE Grading Table, use the grading scheme in this table.

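### SAP 9.7 lists pelvic-exam findings without a by-arm table on the ground that exams are symptom-driven, though the exam is scheduled at every clinic visit; routine yeast wet mounts are also only listed

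*SAP*

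**What the plan says.** SAP 9.7 describes full examinations at screening and symptom-directed ones at all later visits, and draws a reporting rule from that: "Since the evaluations are symptom-driven from enrollment to the end of follow-up, subject listings will be provided for vital signs" (Listing 29), and likewise for physical findings (Listing 30) and pelvic findings (Listing 31). Later in the same paragraph, abnormal discharge and cervical mucus go to Tables 133 to 135, by visit and arm.

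SAP 9.6 has a parallel rule for laboratory tests: "Since the laboratory evaluations are only performed if indicated, subject listings of the clinical laboratory results will be provided". It names the urine dipstick, urinalysis, pregnancy test, HIV and syphilis serology, and the gonorrhoea, chlamydia and trichomonas swab. The wet mount is not among them. A separate sentence, with no reason attached, says "Trichomoniasis and yeast vaginitis wet mount results will be provided in" Listing 28.

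For the follow-up visits, Protocol 4.0 says, and SAP 4.1 repeats, that "a pelvic exam will be performed to detect genital tract AEs". Protocol 7.3 (carried to Visit 3 by 7.4, and repeated in 7.5 and 7.8) includes this step with no condition: "Vaginal swab for wet mount taken from the posterior fornix for yeast vaginitis and clue cells and for amine test (whiff test". Possible product effects in Protocol 2.3.1.1 include "vaginal dryness, genital swelling, rash, vaginal candidiasis (yeast infection".

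**The concern.** The reason in SAP 9.7 is a statement about how the data arise. If only women with symptoms were examined, a by-arm rate would have no clean denominator and a listing would be a sensible choice. If every woman is examined at every clinic visit, that reason falls away.

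Safety is a primary objective, the product is applied vaginally, and candidiasis and genital signs are named possible effects. The staff who perform study assessments are masked (Protocol 5.3.2). A difference between arms in yeast positivity, or in signs seen at examination but not recorded as AEs, would be visible only to someone counting rows in Listings 28 and 31. Listing 31 shows abnormal findings only, so it does not supply the number of women examined.

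**Working it through.** **1. Is the pelvic exam routine?**

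- Appendix A and SAP Table 2 give the symptom-directed physical exam its own row. The pelvic exam and vital signs are separate rows with a plain X at Visits 1 to 4 and 7. The bracketed (X) is reserved for procedures done if indicated.
- Protocol 4.0 and SAP 4.1 place the exam at the follow-up visits to detect genital tract AEs.
- SAP 3.3.1 determines the Amsel criteria during a pelvic exam, and SAP 4.5.2 requires them at each follow-up visit. The primary endpoint therefore needs the exam.
- Against this, the visit text in Protocol 7.3, 7.5 and 7.8 attaches the label symptom-directed to the physical and pelvic exam together. It then orders the speculum exam and swabs unconditionally, and marks only the STI swab, dipstick and pregnancy test as conditional.

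The SAP 9.7 wording probably comes from that label. It conflicts with the other places.

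**2. Is the yeast wet mount routine?** Yes. It has a plain X at the same visits and no condition in the visit text.

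**3. What by-arm output is already planned?**

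| Data | Planned by-arm output | What is left out |
|---|---|---|
| Solicited genital symptoms, including swelling and rash | Tables 108 and 110 | Nothing for this point; source is the participant's memory aid |
| Discharge and mucus at the exam | Tables 134 and 135 | Percentages are among women with evaluable abnormal discharge, and columns stop at Visit 4; the share of examined women is not given |
| Yeast or exam findings recorded as AEs | Tables 126 and 128 | Yeast without symptoms, which Appendix B places in Grade 0: "Absence of symptoms regardless of candida test results"; exam findings not recorded as AEs |
| Wet-mount yeast result | None (Listing 28) | All by-arm counts |
| Other pelvic findings | None (Listing 31) | All by-arm counts |

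**4. How much data?** The planned total is 228 at 2:1, so 228 × 2/3 = 152 and 228 × 1/3 = 76. The total reproduces from the stated assumptions (30% vs 15%, two-sided 0.05, 70% power, no continuity correction): 68 placebo, 68 × 3 = 204, and 204/0.9 = 226.7, rounded up to 227, against 228 stated. Four follow-up clinic visits (2, 3, 4, 7) give up to 152 × 4 = 608 and 76 × 4 = 304 results, 912 in all, or 912 × 0.9 ≈ 821 if 10% are lost.

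**5. What precision would a table have?** The documents give no yeast rate, so the rate p is assumed, equal in both arms, with all women evaluable:

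half-width = 1.96 × √[p(1 − p)(1/152 + 1/76)]

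- p = 0.05: 1.96 × √(0.0475 × 0.01974) = 0.060
- p = 0.10: 1.96 × √(0.09 × 0.01974) = 0.083
- p = 0.20: 1.96 × √(0.16 × 0.01974) = 0.110

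With 10% lost, each is divided by √0.9 = 0.949, giving about 0.063, 0.087 and 0.116. For 80% power against those placebo rates, the LACTIN-V rate would have to be about 18%, 25% or 38%. Such a table is descriptive.

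**The case against.** The strongest reply is that local safety is already well covered. Swelling and rash are solicited and tabulated by arm. Discharge, the effect the protocol calls most likely, has its own tables. AE reporting is mandatory: Protocol 9.2.1 and 9.2.3 require all AEs and abnormal clinical findings to be documented and reported, and Appendix B grades oedema, erythema and lesions from Grade 1. New exam signs and symptomatic yeast should therefore reach Tables 126 and 128. The yes/no AE column in Listing 31 does not prove under-reporting, because a pre-existing finding would properly be marked no. The adopted scale treats yeast without symptoms as normal.

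Most of this stands, and it rules out a tempting reading: that the plan has no by-arm comparison of local harm, or that these are its only masked clinician measures. Neither is supported. Nor can a reader infer that SAP 9.6 wrongly calls the wet mount conditional, since its list does not include it.

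The reply does not restore the premise in 9.7, and it leaves a remainder. A result can fall below the AE threshold and still be worth counting by arm when it is collected on everyone and concerns a named effect. The AE tables also do not use women examined at a visit as their denominator. Counts could be recovered by hand from Listing 28, which shows absent, present and not assessed. Listing 31 gives no denominator.

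**Conclusion.** The concern holds in a limited form. SAP 9.7 rests a reporting rule for pelvic findings on a premise that the Schedule of Events, Protocol 4.0, SAP 4.1 and the endpoint definition contradict. The yeast wet mount is also routine and is only listed, with no reason given. The gap is wet-mount yeast positivity, non-discharge pelvic findings not recorded as AEs, and the share of examined women with abnormal discharge. No primary or secondary result changes; what changes is what the trial can report on local safety.

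The half-widths of about 6, 8 and 11 points depend on assumed rates, equal arms and full follow-up. They describe the precision of a missing table, not the size of an error.

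A reader might infer that every later yeast-positive result is a new infection, because Protocol 7.2 bars randomization of women whose enrollment wet mount shows yeast. That goes too far. A negative wet mount does not prove absence, and SAP 6.3.2.2 provides for randomized women who had a vaginal infection at screening or enrollment. Later positives in women who were negative at enrollment are better described as new since that wet mount.

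**What to change.** 1. Correct the rationale in SAP 9.7 so that it does not describe the pelvic exam as symptom-driven where the schedule makes it routine. Vital signs also carry a plain X, so the same sentence should be checked for them. Reconcile the visit text in Protocol 7.3, 7.5 and 7.8 with Appendix A.
2. Add two descriptive Safety-population tables by arm, at Visits 2, 3, 4 and 7 and cumulatively through Visits 4 and 7: (a) yeast-positive wet mount; (b) any new abnormal pelvic finding since Visit 1, including abnormal discharge, whether or not it was recorded as an AE. Use women examined (for yeast, women with a wet-mount result) as the denominator, and give the between-arm difference with a 95% CI.
3. Keep Listings 28 and 31.

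The cost is some wording and two tables from data already collected. The downside is two more unpowered comparisons, which should be labelled descriptive. No visits, tests or clinical rules change.
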